## 1.6 Talimogene Laherparepvec

Talimogene laherparepvec is an oncolytic immunotherapy based on a modified clinical strain of HSV-1 that has been designed to selectively replicate in cancer cells. Two HSV-1 genes are deleted, ICP47 and ICP34.5. Deletion of ICP47 allows for the presentation of tumor antigens following oncolytic viral replication and enhances anti-tumor immune responses. Deletion of ICP34.5 leads to functional limitations in non-dividing cells and renders the virus non-pathogenic. The human GM-CSF coding sequence is inserted and replaces the gene encoding ICP34.5. This prevents recombination between talimogene laherparepvec and wild-type virus. Additionally, expression of GM-CSF results in local GM-CSF production to recruit and activate antigen-presenting cells [44-46]. Talimogene laherparepvec has gained FDA approval for the local treatment of unresectable cutaneous, subcutaneous, and nodal lesions in patients with melanoma recurrent after initial surgery [47].

### 1.6.1 Pharmaceutical and Therapeutic Background

Nonclinical pharmacology studies, including *in vitro* studies of cytopathic effects and *in vivo* studies of efficacy in numerous tumor types, have been conducted with talimogene laherparepvec and its murine analog, OncoVEXmouse GM-CSF. Talimogene laherparepvec lyses a variety of *in vitro* human tumor cell lines in culture including colorectal cancer (HT29), breast cancer (MDA-MB-231), glioblastoma astrocytoma (U-87 MG), prostate adenocarcinoma (LNCaP), and malignant melanoma (SK-MEL-28) tested at a multiplicity of infection between 0.1 and 5; essentially all tumor cells were killed less than 48 hours following infection *in vitro* [48]. Talimogene laherparepvec affects not only the tumors into which it is injected, but also distant non-injected tumors, demonstrating a systemic beneficial effect from local administration. Talimogene laherparepvec suppresses tumor recurrence upon re-challenge with the same tumor type, and remains effective when animals have undergone previous exposure to wild-type HSV or are immunosuppressed with cyclosporin. Talimogene laherparepvec has been tested to evaluate the combined effects of either radiation or chemotherapy in preclinical studies. Both combinations were tolerated and could support potential clinical studies with these other agents for the treatment of cancer [47].

### 1.6.2 Pre-clinical Findings

Talimogene laherparepvec has been tested for efficacy both *in vitro* and *in vivo* murine tumor models. It has been shown to eradicate or substantially inhibit tumor growth at doses comparable to those used in clinical studies. Nonclinical evaluation

has also confirmed that GM-CSF enhances the immune response generated, enhancing both injected and uninjected tumor responses.

In a B16 melanoma model, irradiated tumor cells alone did not stimulate significant anti-tumor immunity. However, irradiated tumor cells expressing murine granulocyte-macrophage colony-stimulating factor (GM-CSF) stimulated potent, specific, and durable anti-tumor immunity, requiring both CD4+ and CD8+ cells [49]. In murine models with subcutaneous melanoma, intratumoral G-CSF inoculation with inactivated HSV vectors resulted in greater, dose-dependent tumor inhibition and improved mouse survival compared with HSV alone [50].

A number of pre-clinical studies evaluating the safety of talimogene laherparepvec have been completed. Subcutaneous (SC) in mice, single intra-arterial dose in rat, single intraprostatic dose in dogs, and repeated intravenous (IV) dosing in an embryo-fetal developmental in the BALB/c mouse all demonstrated administration safety and tolerable toxicity profiles. The safety of a surrogate HSV-1 construct expressing murine GM-CSF (OncoVEXmGM-CSF) administered as a repeated SC injection was evaluated in BALB/c mice. High and multiple doses of talimogene laherparepvec were well tolerated in immune competent mice following SC, IV, or intralesional injection. A dose margin based on body weight of 60-fold for general safety is estimated using the no adverse effect level. Similarly, a dose margin of 60-fold (based on body weight) for embryo-fetal development is estimated using the NOAEL (also the highest dose tested in Study 117250) following repeated SC injection in mice compared with the maximum dose to be administered to patients [47].

Key findings following repeated SC administration of talimogene laherparepvec included increased white blood cells, lymphocytes, and neutrophils. There was evidence of transient immune activation (enlargement and increased germinal centers in the spleen, lymphoid hyperplasia in spleen and bone marrow). These effects are consistent with the normal response of animals to administration of a virus, and development of normal anti-viral immunity. As a general rule, mice treated with talimogene laherparepvec tended to seroconvert and develop anti-HSV-1 antibodies. No evidence of overt toxicity to any cell type or organ, and no evidence of virally-associated neuropathology/neurovirulence were observed in talimogene laherparepvec-treated animals.

There is no evidence of virally associated neuropathology/neurovirulence associated with talimogene laherparepvec in any animal treated. Two studies found 10,000-fold less neurovirulence at the median lethal dose (LD50) following intracerebral injection of talimogene laherparepvec with deletion of ICP34.5 as compared to wild-type HSV [51, 52]. Additionally, no mortality was seen in mice treated with intranasal talimogene laherparepvec despite use of doses 100-fold greater than those doses associated with the LD50 for wild-type HSV-1 [53].

## 1.7 Rationale for Combination of PD-1 Inhibitors with Talimogene Laherparepvec for MPE

Given talimogene laherparepvec's efficacy and favorable toxicity profile as monotherapy, pre-clinical studies have evaluated combining talimogene laherparepvec with other immune-activating agents [54]. In pre-clinical studies in a melanoma mouse model, an oncolytic virus induced both local and distant tumor infiltration with CD4+ and CD8+ T cells. The addition of CTLA-4 blockade induced significant anti-tumor responses and protection from tumor re-challenge [55]. In a phase Ib study, the efficacy of talimogene laherparepvec plus ipilimumab was assessed in advanced melanoma. In 19 patients evaluated, there were no dose limiting toxicities. Objective response rate was 50% with 44% of patients achieving durable response lasting more than 6 months. Additionally, 18 month PFS and OS were 50% and 67%, respectively [56].

Currently, combination therapy with talimogene laherparepvec and pembrolizumab is being investigated in two human populations: unresected melanoma and recurrent metastatic HNSCC. A two-part phase 1b/3 study is being conducted in patients with unresectable stage IIIB-IV melanoma to evaluate the safety of talimogene laherparepvec in combination with pembrolizumab versus pembrolizumab alone. The phase 1b portion of the study was single armed evaluating safety of talimogene laherparepvec and pembrolizumab combination. Twenty-one patients received intralesional injections of talimogene laherparepvec on a dose-escalation basis up to  $\leq 4$  mL at  $10^8$  PFU/mL dose every 2 weeks. Pembrolizumab 240mg IV every 2 weeks was initiated at 5 weeks after the initial talimogene laherparepvec dose. Treatment was continued until disease progression per immune-related response criteria (irRC), no injectable lesions, study treatment intolerance, or 2 years of treatment. No DLTs were reported and seven patients reported treatment-related Grade 3 adverse events. Of the 21 patients in the phase 1b study, results yielded confirmed ORR (57.1%), CR rate by irRC (23.8%), and disease control rate (71.4%). The phase 3 study investigating the safety and efficacy of talimogene laherparepvec in combination with pembrolizumab versus pembrolizumab alone is currently underway [47, 57]. Additionally an NCI-led Phase II trial has been proposed for combination talimogene laherparepvec and nivolumab in refractory T-cell lymphoma and advanced non-melanoma skin cancers.

Based on these observations, we propose to conduct a Phase II trial that includes a safety run-in cohort to investigate the novel approach of administering intrapleural talimogene laherparepvec via a pleurX catheter in patients with known MPE. After establishing the safety of this approach, we plan to treat a total of 24 patients with MPE's with intrapleural talimogene laherparepvec and IV nivolumab. We hypothesize that patients receiving this novel combination will achieve resolution 70% of the time compared to the null hypothesis of 45% with pleur-x catheter alone. In addition, we plan to conduct correlative studies using pleural cytology and blood samples as outlined below.

In clinical practice, chemotherapy (bleomycin) and irritant agents (such as talc) have been administered to the pleural space. Out of an abundance of caution, we conduct a phase I study as described to ensure safety while infusing talimogene laherparepvec. However, we note that knowledge of the mechanism of action and previous safety data with subcutaneous injection suggest low risk of novel adverse events from this mechanism of injection. Further, phase I data of the combination of subcutaneous talimogene laherparepvec further support the safety of this combination [58].

## 1.8 Correlative Studies

We hope to define changes in the tumor immune microenvironment elicited by combination of intrapleural talimogene laherparepvec and IV Nivolumab therapy in patients with malignant pleural effusions. The tumor immune microenvironment is a complex mixture of competing cellular phenotypes. Thus an optimal predictor of response to immunomodulatory therapy will likely include features that describe tumor genetics, tumor-related immunosuppression, and any existent but insufficient anti-tumor immune response. Correlative studies will be run in both pleural fluid and blood samples.

We hypothesize that (1) patients treated with nivolumab + talimogene laherparepvec will show increased effector lymphocytic infiltrates, decreased regulatory cell populations, and increased clonal expansion of tumor-infiltrating T cells; moreover, (2) a robust integrated model that predicts response vs. resistance can be made from a set of key clinical, tumor, and immune features.

### 1.8.1 Aim 1

Pleural fluid and blood samples will be analyzed by flow cytometry at three time points: pre-treatment, 3 weeks post initial therapy, and 9 weeks post initial therapy. Pleural fluid derived single-cell suspensions will be stained with fluorescently-labeled antibodies to quantify cytotoxic T cells, effector helper T cells, and regulatory T cells. Regulatory T cells will also be sub-fractionated into naïve, effector, effector memory, and central memory. T cells will also be analyzed for the expression of regulatory proteins PD1 and CTLA4. B cells will be quantified as naïve vs. activated. We will also quantify myeloid-derived suppressor cells and tumor-associated macrophages. Non-naïve T cells and B cells will be sorted and TCR $\beta$ /IgH repertoires will be amplified and sequenced. Lymphocyte subset frequencies and TCR $\beta$ /IgH repertoires from peripheral blood will be evaluated for similarity with tumor and controls using the Morisita-Horn index and Kruskal-Wallis significance testing.

### 1.8.2 Aim 2

We will perform RNA sequencing and whole exome sequencing (WES) to analyze the tumor and local pleural immune microenvironment by gene expression profiling on pre-treatment samples. RNA and DNA will be extracted from pleural fluid samples. mRNA-Seq libraries will be made and sequence data will be processed,

filtered, and aligned and transcript abundance quantitated. DNA libraries will be made to perform whole exome sequencing. Determination of molecular subtypes and relative expression of gene signatures associated with immune cellular and functional phenotypes along with inference of T cell and B cell receptor repertoire characteristics from mRNA-seq data will be performed. We will consider the following features as potential determinants of response: age, performance status, smoking status, tumor type and histology, total dose of nivolumab and talimogene laherparepvec received, molecular subtype, expression of PD-1 ligands, expression of immune phenotypic gene signatures, and TCR $\beta$ /IgH repertoire characteristics.

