## 4.0 TREATMENT PLAN

### 4.1 Schema for LCCC 1626

Talimogene laherparepvec (TVEC) will be given intrapleural (IP) instillation for up to 9 cycles (includes seroconversion dose 4ml of 10^6 pfu/mL) in Dose Level cohorts 1 and 2. Nivolumab (240 mg IV) will be co-administered with talimogene laherparepvec (4ml of 10^8 pfu/mL) for up to 9 cycles in the Dose Level 2 cohort, with 3 week interval between cycle 1 and cycle 2 to allow for seroconversion. Patients will be allowed to continue nivolumab monotherapy per standard of care (240 mg IV Q2W) as long as they are responding to therapy (i.e., until disease progression, untoward toxicity, or withdrawal for other reasons).

This Phase Ib/II trial includes a safety run-in period using 3 + 3 dose escalation rules to evaluate the feasibility of administering talimogene laherparepvec into the intrapleural space of patients with MPE via a pleurX catheter. All infusions of talimogene laherparepvec will occur in 200cc normal saline (NS) followed by 20cc of sterile saline to clear the catheter, regardless of dose. Subjects will be instructed to avoid drainage for at least 24 hours, then to drain the catheter (and flush with 20 cc of sterile saline) when next needed to palliate shortness of breath, consistent with standard of care use of the pleurX catheter. If a patient becomes dyspneic <24 hours after talimogene laherparepvec administration, they should consult the interventional pulmonology team at UNC to determine if catheter drainage is necessary. Patients who experience severe shortness of breath <24 hours after

intrapleural talimogene laherparepvec will be allowed to have their catheter drained.

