In Dose Level 2 (expected Phase II dose), the first 3 patients will receive both IP talimogene laherparepvec and IV nivolumab. The first dose of talimogene laherparepvec will be administered on Cycle 1, Day 1 at 4mL of  $10^6$  pfu/mL in 200 cc normal saline (IP) to seroconvert HSV-seronegative patients. Three weeks will be given for seroconversion. Subsequent doses of talimogene laherparepvec at 4ml of  $10^8$  pfu/mL + Nivolumab 240 mg IV will be administered every two weeks starting on Cycle 2, Day 1 for up to 8 cycles of therapy. Patients will be assessed for DLTs related to IP administration of talimogene laherparepvec after seroconversion and 2 cycles of combination therapy (i.e., 7 weeks of study treatment). If  $\geq 2$  patients experience DLT, the study will be discontinued. If 1 patient out of 3 has DLT, 3 additional patients will be recruited and treated at the same dose level. If 0 out of 3 or  $\leq 1$  patient out of 6 has a DLT in the dose level 2 cohort, the study will recruit additional patients in Phase II at this dose level and accrue a total of 24 patients as per study goal. All patients treated at dose level 2 in Phase I or Phase II, will be included in analyses of safety and efficacy. Safety stopping rules will ensure the safety of subjects receiving combination treatment in Phase II (see [Statistical Considerations in section 9.0.](#))

Subjects may continue talimogene laherparepvec for up to 9 cycles (i.e. alone or with nivolumab) until resolution of pleural effusion or they experience systemic disease progression. Subjects who have resolution of pleural effusion as defined by

the primary endpoints may continue nivolumab monotherapy per standard of care until disease progression (see section 4.2 for details on treatment and section 6.5.2).

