## 4.2 Study Treatments

Agent	Pre-medications	Dose/Frequency	Route	Schedule
talimogene laherparevec (1 st dose only) 	30 min prior to IP talimogene laherparevec give anti-pyretic & anti-nausea meds (e.g., 500 mg	$4 \times 10^6$ pfu; next dose of talimogene laherparevec given 3 weeks later	via pleurX catheter and allow product to dwell for at least 24 hours	D1 cycle 1 only; subsequent dose given three weeks later
talimogene laherparevec (Subsequent doses) 	acetaminophen & 10 mg prochlorperazine)	$4 \times 10^8$ pfu every 2 weeks X 8 doses	via pleurX catheter and allow product to dwell for at	D1 cycle 2 of study for up to 8 cycles given every 2 weeks (14 days)

			least 24 hours	until fluid stops re-accumulating (i.e., resolution of pleural effusion) or until systemic disease progression
Nivolumab	See section 4.3.3 for management of infusion-related reactions associated with nivolumab	240 mg every 2 weeks	IV over 30 minutes	Starting on D1 of Cohort 2 Dose Level 2 and beyond; Every 2 weeks (14 days) until disease progression (per RECIST or irRC) or withdrawal for other reasons

1. [See Appendix D](#) -Information Sheet for Caregivers, Family Members or other Close Contacts to Clinical Trial Participants being given Talimogene Laherparepvec).

Talimogene laherparepvec (4 mL) at a concentration of  $10^6$  (1 million) plaque-forming units (pfu)/mL will be administered into the pleurX catheter for a total dose of  $4 \times 10^6$  pfu for the first dose. Subsequently, talimogene laherparepvec (4 mL) at a concentration of  $10^8$  (100 million) pfu/mL will be administered every two weeks into the pleurX catheter. Dosing with talimogene laherparepvec will be continued until pleural fluid stops re-accumulating or until systemic disease progression. Subjects who have resolution of pleural effusion as defined by the primary endpoints may continue nivolumab monotherapy per standard of care until disease progression. The dose rationale for talimogene laherparepvec therapy is based on the OPTiM trial in melanoma and subsequent analysis [44, 61].

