### 4.3 Dose Modifications/Delays

#### 4.3.1 Talimogene laherparepvec Dose Modifications/Delays

There will be no dose modifications allowed for talimogene laherparepvec during the study. Talimogene laherparepvec will be administered as described in section 4.2 above. Talimogene laherparepvec administration will either be withheld or permanently discontinued depending on the severity of event related to its administration. If a grade 4 DLT occurs, talimogene laherparepvec will be permanently discontinued. If grade 3 DLTs occur with talimogene laherparepvec administration as described in section 4.1.2 (Definition of DLTs), the next dose of talimogene laherparepvec will be withheld and will not be given until symptoms have resolved to  $\leq$  grade 1. If  $> 1$  scheduled dose of talimogene laherparepvec is missed due to toxicity, talimogene laherparepvec will be permanently discontinued.

Doses up to 4 mL at dose strength of  $10^8$  pfu/mL every 2 weeks (maximum cumulative dose of  $222.5 \times 10^8$  pfu) have been administered in clinical studies, with no evidence of DLT. The maximum cumulative dose of talimogene laherparepvec planned for this trial is 9 total administrations (including initial seroconversion dose). See section 5.1.6, for warnings and precautions related to talimogene laherparepvec administration. Patients may receive premedication with an anti-pyretic and anti-nausea medication (e.g., acetaminophen 500mg PO and prochloraperizine 10mg PO) prior to every talimogene laherparepvec injection.

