#### 4.5 Duration of Therapy

In the absence of treatment delays due to AEs, treatment may continue until the end of study-defined treatment or until:

- Disease progression (Note: treatment may continue until progression is confirmed by repeat scan approximately 6 weeks later to rule out pseudoprogression based on investigator discretion)
- Inter-current illness that prevents further administration of treatment
- Unacceptable toxicity
- Pregnancy
- Patient decides to withdraw from study treatment, **OR**
- General or specific changes in the patient's condition render the patient unacceptable for further treatment in the judgment of the investigator.

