### 5.2.4 Dose, Schedule and Administration

See section 4.3.2

Nivolumab will be given every two weeks at a dose of 240 mg to be administered as a 30 minute IV infusion.

Subjects may be dosed no less than 12 days from the previous dose of drug. There are no premedications recommended for nivolumab on the first cycle.

Subjects should be carefully monitored for infusion reactions during nivolumab administration. If an acute infusion reaction is noted, subjects should be managed according to institutional guidelines (See section 4.3.3).

Doses of nivolumab may be interrupted, delayed, or discontinued depending on how well the subject tolerates the treatment.

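### Aim 2 lists total dose received as a determinant of response with no exposure window, although resolution and progression help set that dose

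*Combined protocol and SAP*

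**What the plan says.** Section 1.8 hypothesizes that "a robust integrated model that predicts response vs. resistance can be made from a set of key clinical, tumor, and immune features". Section 1.8.2 (Aim 2) then names the candidate features. Most are fixed at baseline (age, performance status, smoking, tumor type), and Aim 2's gene-expression profiling is done on pre-treatment samples. One item is different in kind: "total dose of nivolumab and talimogene laherparepvec received". No cut-off time is attached to it there, in exploratory objective 2.3.3, or in Section 8.3, which describes no correlative model.

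The treatment rules that determine this quantity are:

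- **Virus, duration.** Up to 9 administrations, given "until resolution of pleural effusion or they experience systemic disease progression" (Section 4.1.1). Section 4.2 repeats the rule: "Dosing with talimogene laherparepvec will be continued until pleural fluid stops re-accumulating or until systemic disease progression".
- **Virus, dose level.** "There will be no dose modifications allowed for talimogene laherparepvec during the study" (Section 4.3.1).
- **Nivolumab, duration.** Section 4.1 lets it continue "as long as they are responding to therapy (i.e., until disease progression, untoward toxicity, or withdrawal for other reasons"). Section 4.2 lets resolvers go on with it until progression. Section 4.5 adds that "treatment may continue until progression is confirmed by repeat scan approximately 6 weeks later", at the investigator's discretion.
- **Nivolumab, dose level.** Fixed at 240 mg. "Doses of nivolumab may be interrupted, delayed, or discontinued depending on how well the subject tolerates the treatment" (Section 5.2.4).

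Section 1.8.2 does not define response. Sections 2.2.3 and 2.4.2.3 use irRECIST (irCR+irPR), while Section 8.2 uses the word for effusion resolution, the Phase II primary endpoint in 2.4.1.2.

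**The concern.** Because the dose level of neither agent is adjusted, total dose is mainly a count of cycles on treatment. The events that end those cycles include resolution (virus) and progression (both agents). A predictor partly produced by the outcome tends to show an association when dose does nothing. It is also unknown before treatment starts, so it cannot serve a model meant to predict response from patient and tumor features.

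At stake is how an exploratory model is read. Entered as listed, total virus dose could suggest that less virus goes with resolution, when the stopping rule alone produces that pattern. No primary, secondary or safety analysis uses this feature.

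**Working it through.** **1. The plan's own figure (context only).** Aim 2 states no sample size, so N = 24 comes from Section 8.2: 45% against 70%, two-sided 0.10, 80% power. n = [(1.645·√(0.45·0.55) + 0.842·√(0.70·0.30)) / 0.25]² = 23.2, rounded up to 24. Power at 24 is 81.2%. The figure reproduces and is not in dispute.

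**2. Virus count if response means resolution, by hand.** Assume, per cycle, resolution 0.10 and progression 0.05, independent of dose and of each other, with same-cycle ties going to progression. Resolution is counted only before progression. These rates are not in the documents.

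- Chance of continuing past a cycle: q = 0.90 × 0.95 = 0.855; q⁹ = 0.244.
- Share resolving within 9 cycles: (0.95 × 0.10 / 0.145) × (1 − 0.244) = 0.495.
- Mean virus doses in resolvers: 1/0.145 − 9 × 0.244/0.756 = 3.99.
- Mean over all patients: 0.756/0.145 = 5.21.
- Mean in non-resolvers: (5.21 − 0.495 × 3.99)/0.505 = 6.41.

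Resolvers receive about 2.4 fewer virus doses although dose has no effect.

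**3. Range of assumed rates, response = resolution.** The simulations crossed per-cycle resolution 0.10/0.15/0.20, progression or death 0.05/0.10/0.20 and other stopping 0/0.05. Nivolumab was counted from cycle 2 and capped at 26 doses. Dose had no effect. A false signal is p < 0.05 in a two-sided Mann-Whitney test of total dose, resolvers against non-resolvers, N = 24. The plan names no test for this. The results depend on when resolution still counts:

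| Resolution is counted | Virus false signals | Nivolumab false signals |
|---|---|---|
| Only before progression or stopping (36 settings, both tie rules) | 4–54% | 19–91% |
| Up to two cycles after stopping (18 settings) | 4–64% | 12–30% |
| Through cycle 9 regardless of progression (18 settings) | 18–82% | 2–6% |

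In the first row, resolvers averaged 0.1–2.6 fewer virus doses and 2.7–8.6 more nivolumab doses. The virus signal there was 8–54% at 5% progression per cycle, 5–17% at 10%, and 4–5% (chance) at 20%. In the five settings nearest the 70% alternative (67–76% resolving), it was 11–38% for virus and 29–60% for nivolumab. Resolvers had fewer virus doses under all three counting rules. In the last row, the mean nivolumab difference was about zero.

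**4. A limit on the virus direction.** It is a tendency. Suppose instead that resolvers are fixed in advance, resolve at 10% per cycle, and are not cut short by progression, while non-resolvers progress at 30% per cycle. Resolvers then average 10 − 9 × 0.9⁹/(1 − 0.9⁹) = 4.3 virus doses and non-resolvers (1 − 0.7⁹)/0.3 = 3.2. Rapid progression can reverse the sign.

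**5. Response = irCR+irPR.** Scans were placed before cycle 5 and every 4 cycles after (Section 6.2), with assumed response probabilities per scan. Nivolumab false signals were 57–99% over 6 settings. Virus false signals were 3–38%, with responders averaging from 5.88 − 3.69 = 2.2 more doses to 5.99 − 4.27 = 1.7 fewer, depending on how closely tumor response tracks resolution.

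**6. A landmark count.** Patients still at risk number 24 × [(1 − resolution)(1 − progression)(1 − other)]^k after k cycles. The per-cycle factor runs from 0.80 × 0.80 × 0.95 = 0.608 to 0.90 × 0.95 = 0.855. At C3D1 (k = 2) this gives 8.9 to 17.5 patients; at C4D1 (k = 3), 5.4 to 15.0. In a separate run (per-cycle resolution 0.10–0.30, progression 0.05–0.20) with a cycle-3 landmark and an assumed 15% of doses missed at random, false signals were about 1–4%, no excess over 5%.

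**The case against.** **The nivolumab link to resolution is not in the documents.** A reader might infer from the stopping rules that resolvers must accumulate more nivolumab. The text does not support that. The endpoint has no progression cut-off, drainage is every other day, and the diary is still scheduled at the end-of-treatment visit, 30 days after the last dose. The 45% null is for the catheter alone, so resolution need not depend on continued dosing. The table bears this out: counting resolution through cycle 9 regardless of progression takes the nivolumab signal to chance. Death does preclude resolution, so the truth may lie between the rows. This objection stands, and the nivolumab limb is conditional on it.

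**The ranges are wide and rest on assumed rates.** This is also fair. In 15 of the 36 settings fewer than 45% resolve, below the plan's own null. The 91% falls to 63% when only the tie rule changes. These are illustrations, and a reader should not take them as the trial's error rates.

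**The list is only a set of candidates.** Section 1.8.2 says the features will be considered, 2.3.3 is exploratory, and 8.3 specifies no model. A reader might infer that the team has committed to entering lifetime dose; it has not. But this list is the only description of the model's inputs, and nothing elsewhere adds a window.

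**Deletion is not the only repair.** Correct: a landmark or time-dependent exposure would also be valid.

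**Conclusion.** The point holds as a minor one. Total dose without an exposure window is not a valid predictor of response here, because the outcome helps set it.

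- **Response = resolution, virus.** The link is direct, since resolution ends virus dosing. Resolvers tend to show fewer doses. False signals ran from chance level to about 80%, depending on the assumed rates and the counting rule.
- **Response = resolution, nivolumab.** An association arises only so far as progression, death or stopping prevents resolution from occurring or being counted. The documents do not say. The signal ranged from chance level to about 90%.
- **Response = irCR+irPR.** The nivolumab count reflects time without progression; the virus direction is not established.

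The dependence of dose on outcome follows from the treatment rules. The sizes rest on assumed constant per-cycle rates, a 26-dose nivolumab cap and a test that the plan does not name. Nothing here touches the primary test, its sample size, the secondary endpoints or safety.

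**What to change.** In Section 1.8.2:

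1. Delete "total dose of nivolumab and talimogene laherparepvec received" from the list of determinants.
2. Add a sentence such as: *Total dose received will be summarized descriptively by response group and will not be entered as a predictor of response.*
3. State whether response in Aim 2 means resolution (2.4.1.2) or irCR+irPR (2.4.2.3).

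If exposure-response is still wanted, use only dose received before a fixed landmark among patients still at risk, or a time-dependent exposure, and accept the small numbers. Since virus dose is not modified, patients at risk at the same landmark will differ mainly through missed or delayed doses, so there will be little contrast to study.

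The cost is one item deleted, one sentence added and one definition stated, with no change to dosing, visits, data collection or sample size. The loss is a formal total-dose exposure-response model, which unaligned total dose could not validly support.
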